- 2) Freedom from MALE
- 3) Target vessel and/or bypass patency
- 4) Survival at 1, 3 and 5 years

STUDY DESIGN

This study is a two phase, single-center, non-blinded randomized controlled trial. The first phase of the trial will include 20 patients; 10 assigned to post-operative exercise rehabilitation and 10 to best medical therapy. The primary objective of Phase I is to assess for feasibility and safety of this randomized controlled trial in CLI patients after revascularization. We will assess rate of enrollment, adherence to the exercise regimen and any unforeseen barriers or challenges that patients may encounter with the rehabilitation program.

If Phase I of the trial confirms that the exercise program is feasible and safe for CLI patients post-revascularization, we will proceed with Phase II of the trial. The primary objective for Phase II is to determine if a supervised exercise rehabilitation program will improve walking distance after revascularization compared with patients treated with best medical therapy. Phase II will also compare quality of life outcomes between the two groups.

STUDY POPULATION

The population to be studied in this group is patients with PAD and CLI Fontaine classification III and IV. This means that these patients will have ischemic rest pain in their legs and/or non-healing ischemic ulcers on their feet.

ENROLLMENT

Patients will be identified on a referral basis through our outpatient vascular surgery clinic. The seven practicing vascular surgeons in Calgary will be informed of the current study. Patients who have undergone revascularization for CLI will be identified for consideration of participation in this study within six months of their procedure. All surgical and ischemic wounds to be deemed sufficiently healed prior to assessment for fitness in the study. Once the attending vascular surgeon considers the patient fit to participate, the research coordinator will assess the patient for possible inclusion in the study.

Inclusion Criteria

- 1) Ambulating prior to procedure
- 2) Living independently prior to procedure
- 3) Available to attend all SEP and follow-up appointments
- 4) PAD Fontaine class III and IV (rest pain and tissue loss)
- 5) Entry with consent of vascular surgeon
- 6) Ischemia secondary to TASC A-D lesions identified on imaging (CTA or angiogram)
- 7) Able to understand and sign informed consent
- 8) >18 years of age

Exclusion Criteria

- 1) Confined to wheelchair

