- 2) Patients with exercise tolerance limitations due to other co-morbidities such as cardiorespiratory, musculoskeletal, or peripheral neuropathy. (NYHA class III and IV)
- 3) PAD Fontaine class I and II (asymptomatic, claudication)
- 4) Patients with ongoing tissue loss that limits ambulation
- 5) Patient with previous revascularization procedures
- 6) Patients undergoing revascularization for acute limb ischemia events

SAMPLE SIZE

There are currently no data evaluating outcomes of post-revascularization supervised exercise programs in patients with critical limb ischemia, however these studies have been completed in claudication

patients. Studies on PAD claudication (Fontaine class II) patients who have undergone revascularization followed by SEP have all shown significant improvement in functional capacity compared with best medical therapy alone. These previous studies that showed consistently a 20% greater increase in walking distance in the post-revascularization SEP group compared with Best Medical Therapy (BMT) post-revascularization. Given this previous data, 64 patients are required to have a 80% chance of detecting, with a two-sided significance of 0.05, an increase in the primary outcome measure of a 20% greater increase in distance for the 6MWT in the experimental group compared with the control group. Final sample size will be adjusted for expected attrition.

METHODS

INTERVENTION

Patients included in the study will be identified in the vascular surgery outpatient clinic or through Emergency department as requiring revascularization secondary to critical limb ischemia. Patients will be approached regarding study participation prior to the revascularization procedure. After eligibility is confirmed and patients have signed informed consent, patients will be randomized to one of two groups:

- 1) Best Medical Therapy (BMT)
- 2) BMT + Supervised Exercise Program (SEP)

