Functional Capacity:

In order to assess functional capacity, we will measure walking performances at the first exercise session and after 12 weeks. Walking performance will be measured using a six-minute walk test (6MWT) (Guyatt et al, 1985) which has been validated in the functional evaluation of chronic disabling disease, more specifically in patients with PAD (Gardner, Montgomery, & Parker, 2012; McDermott et al., 2009). For this test, the patients will be made to walk on a flat surface for 6 minutes and total distance covered will be recorded by the test administrator. Patients will also undergo a graded treadmill test to evaluate maximum walking distance (MWD) and pain-free walking distance (PFWD). The treadmill is set at a constant speed of 3.2km/hr and starts at an incline of 0%, increasing by 2% every 2 minutes until an incline of 10% is reached or the patients stops the test (Gardner et al., 2012). This test is also commonly used and has been validated in PAD patients.

Quality of Life (QoL):

Validated generic and PAD-specific QoL questionnaires will be administered at the first and final visits. The Short Form 36 (SF-36) and VascuQol. The SF-36 is a generic health status questionnaire, while the VascuQol is a quality of life questionnaire validated for patients with PAD.

Given that this is a pilot study to assess the feasibility in exercise rehabilitation in this population that is considered end-stage PAD, we want to capture major challenges or barriers for these patients. As such, we will also perform an interview and survey at the mid-term and at the completion of exercise program for the SEP group to collect information around challenges associated with the rehabilitation.

Limb Hemodynamics:

Ankle brachial index (ABI) measurements will be recorded at initial assessment and 12 weeks as a measure of peripheral arterial blood flow. ABI is obtained by measuring the highest systolic pressure at the ankle over the highest systolic pressure in the arm. We will use a handheld Doppler probe and blood pressure cuff to collect these measurements. We will also use duplex arterial ultrasound at 2 weeks post intervention and again at 12 weeks to monitor patency of revascularization.

RANDOMIZATION

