Microsoft Excel will be used to generate a block randomization sequence for Phase I (20 patients) followed by a block randomization sequence for Phase II (44 patients) of the study. Patients who are eligible to participate in the study will be stratified by sex and randomized to either SEP or BMT. Block sizes of 4 and 6 will be used to prevent anticipation of the randomization sequence.

ALLOCATION CONCEALMENT

Once the random block sequence has been generated, allocation cards will be created and sealed in sequentially numbered opaque envelopes. The envelopes will be stored in a secured filing cabinet in the vascular surgery research office. The envelopes will be opened sequentially after a patient consents to participate in the study.

DATA COLLECTION

No study data will be collected until patients have reviewed and signed the informed consent. Opportunity to ask questions and have time independent from study team will be provided.

Data will be recorded using Excel spreadsheets. Medical outcomes and complications will be tracked using Vascubase software. Data will be stored on Alberta Health Services computers to maintain patient confidentiality.

STATISTICAL ANALYSIS

Normally distributed data will be presented as mean \pm SD. Results at baseline and 12 weeks will be compared using a paired t-test. For data that is not normally distributed, comparisons will be performed using a non-parametric Mann-Whitney test. Comparisons will be accepted as statistically significant at 95% confidence level ($p \leq 0.05$). STATA software will be used for statistical analysis.

ETHICAL CONSIDERATIONS

Patients who are randomized to the SEP group will be provided with tri-weekly visits for supervised exercise guidance and support. Patients will receive reimbursement for travel to and from the exercise facility. This will include refunds for gas, parking or other required transportation (taxi, public transport, etc).

FOLLOW UP OF PATIENTS WITHDRAWN FROM STUDY

Patients who withdraw or do not complete the program will be contacted and interviewed at the end of the 12 week study period to understand why they were unable to complete the training program.

LIMITATIONS

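### As most naturally read, the fallback for the paired t-test on non-normal data is the Mann-Whitney test, which is for independent samples; it can miss within-patient change but does not inflate false positives

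*Combined protocol and SAP*

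**What the plan says.** The Statistical Analysis section describes one comparison: "Results at baseline and 12 weeks will be compared using a paired t-test". The next sentence is the fallback: "For data that is not normally distributed, comparisons will be performed using a non-parametric Mann-Whitney test". The one after sets the threshold for all testing: "Comparisons will be accepted as statistically significant at 95% confidence level". No signed-rank test is named anywhere, and the section does not define which comparisons the fallback covers.

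The data are paired by design. Under Pre/Post Testing, for functional capacity, "we will measure walking performances at the first exercise session and after 12 weeks". Quality of life and ankle brachial index are likewise taken at the start and end in the same patients.

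The sample size is set for a different, between-arm question: a "20% greater increase in distance for the 6MWT in the experimental group compared with the control group".

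**The concern.** The Mann-Whitney test assumes two independent samples. Baseline and 12-week values from the same patients are not independent, and the rank counterpart of the paired t-test is the Wilcoxon signed-rank test. Applied to the two sets of values, Mann-Whitney ignores the pairing. Its reference distribution is then too wide whenever a patient's two values are positively correlated, and its p-values are too large.

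Walking distances and questionnaire scores may well be skewed or bounded, and samples are small: 10 per arm in Phase I and about 32 per arm over both phases. Outcomes judged non-normal would take this route. At stake is whether a real gain within an arm is reported as non-significant, in a pilot meant to inform a broader trial.

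**Working it through.** **Inputs from the documents.**
- Phase I allocation: "10 assigned to post-operative exercise rehabilitation and 10 to best medical therapy", so 10 per arm.
- Total: "block randomization sequence for Phase I (20 patients) followed by a block randomization sequence for Phase II (44 patients"). 20 + 44 = 64, or 32 per arm at 1:1, before any attrition.
- Level: 0.05, two-sided (Sample Size section).

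**The plan's own figure.** The Sample Size section states "64 patients are required to have a 80% chance of detecting, with a two-sided significance of 0.05". With no SD given, 64 cannot be reproduced, only inverted. For 32 per arm the detectable standardised difference is (1.960 + 0.842) × √(2/32) = 0.70, which is an SD of 20/0.70 ≈ 28.6 if the difference is read as 20 percentage points. This is a two-arm calculation and does not depend on the within-patient test.

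**Assumptions, because the documents give no figures.** Correlation ρ between a patient's baseline and 12-week values: 0.5 to 0.8, with 0 for reference. Within-patient change: 0, 0.4 or 0.8 baseline SD on normal data, or a 20% rise on log-normal data with coefficient of variation (CV) 0.3 or 0.5.

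**Why an unpaired test is conservative here.** Take means as a guide, since rank tests behave similarly. For n patients and a change of δ SD, an unpaired test statistic has mean δ√(n/2). Its actual variance is 1 − ρ, but the test takes it to be 1. So:
- Rejection under no change = 2Φ(−1.96/√(1 − ρ)). For ρ = 0.5 this is 2Φ(−2.77) = 0.6%; for ρ = 0.8 it is 2Φ(−4.38), essentially 0.
- Unpaired power ≈ Φ[(δ√(n/2) − 1.96)/√(1 − ρ)]. For n = 32 and δ = 0.4, δ√(n/2) = 1.6. Power is Φ(−0.36/0.707) = 31% at ρ = 0.5 and Φ(−0.36/0.447) = 21% at ρ = 0.8.
- Paired power ≈ Φ[δ√n/√(2(1 − ρ)) − 1.96]. For the same case it is Φ(2.26 − 1.96) = 62% and Φ(3.58 − 1.96) = 95%.

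The unpaired test reaches 50% power only when δ√(n/2) = 1.96. That is δ = 1.96/4 = 0.49 SD with 32 patients and 1.96/2.236 = 0.88 SD with 10. This is why the loss depends so strongly on the unknown size of the change.

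**Simulation of the two rank tests** (thousands of runs per setting, ρ = 0.5 to 0.8; repeat runs differ by a point or two):

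| Setting | Mann-Whitney | Signed-rank |
|---|---|---|
| No change, 10 or 32 patients | about 0 to 1% | about 5% |
| 32 patients, 0.4 SD | 21 to 27% | 58 to 93% |
| 32 patients, 0.8 SD | 93 to 99% | nearly 100% |
| 32 patients, 20% rise, CV 0.3 | 70 to 80% | 91 to 100% |
| 32 patients, 20% rise, CV 0.5 | 19 to 25% | 51 to 88% |
| 10 patients, 0.4 SD | 3 to 7% | 21 to 41% |

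The SD-based rows use normal data, which the plan would send to the paired t-test. The log-normal equivalent of the second row (a shift of 0.4 SD on the log scale) gives 22 to 27% against 50 to 86%, a somewhat smaller contrast.

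At ρ = 0 the tests perform alike: 66% against 64% for 32 patients, a 20% rise and CV 0.3.

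**Between arms.** Mann-Whitney on change from baseline, SEP against BMT, 32 per arm, CV 0.3, ρ = 0.5 to 0.9: rejection under no difference is 4.4 to 4.8%. The test is sound for that purpose.

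**The case against.** The strongest reply is that *comparisons* need not mean baseline against 12 weeks. The hypotheses, the Phase II objective and the sample size all concern SEP versus BMT, where Mann-Whitney is valid, and the section uses the same word for all testing in its next sentence. It is therefore not established that patients' paired values will be analysed as two independent groups. That stands as a limit on certainty, but it does not rescue the text. On that reading nothing is named for non-normal paired data. Normal outcomes would be tested for change within patients and non-normal ones for a difference between arms, so the shape of the data would decide the question.

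A second reply is that the loss of power follows from the chosen inputs. That also stands. With 32 patients it runs from negligible at a 0.8 SD change to severe at 0.4 SD. Among the settings tabulated, power is lowest with 10 patients, but Phase I is designed for feasibility and safety, not efficacy.

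A third reply is that the fault is harmless to the main conclusion. It is conservative, touches only within-arm results judged non-normal, and within-arm change does not answer the hypothesis: both arms receive revascularization and best medical therapy, so either may improve without the exercise program. This stands and limits the severity.

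**Conclusion.** The point holds as a mismatched or ambiguous fallback test that should be corrected before analysis. On the plain reading, an unpaired test replaces a paired one. On the alternative reading, a paired test is missing and the normality check switches the question. If Mann-Whitney is applied to paired data with correlation 0.5 to 0.8, its error rate falls from 5% to about 0 to 1%. Its loss of power with 32 patients ranges from slight to large according to the size of the change and the variability. All these figures rest on assumed correlations, changes and variability.

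A reader might infer that real within-patient change will largely be missed, or that the p-values will be far too large whatever the data. The documents do not support either as a general statement: they give no SD, correlation or expected change, there is no loss at correlation 0, and power stays at 70 to 80% for a 20% rise with CV 0.3 and 32 patients. A reader might also infer that the trial's main conclusion is compromised. It is not: false positives are not inflated, and neither the between-arm question nor the sample size of 64 depends on this sentence. The accurate statement is that within-patient gains *can* be missed for outcomes judged non-normal.

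**What to change.** Replace the fallback sentence in the Statistical Analysis section with:

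> For within-patient comparisons of baseline and 12 weeks that are not normally distributed, the Wilcoxon signed-rank test on the paired differences will be used. The Mann-Whitney test will be used only to compare independent groups (SEP versus BMT) on the change from baseline to 12 weeks.

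This settles both readings. The cost is one sentence replaced by two; no new data are needed, and the signed-rank test is a standard STATA command.

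The edit does not supply the primary between-arm analysis, which is the larger gap and needs its own specification: the section names no SEP-versus-BMT test for normally distributed data. One option is analysis of covariance of 12-week 6MWT distance, adjusted for baseline distance and for sex, the stratification factor. Both changes are best made together, before any outcome data are analysed.

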Exercise training is a proven effective treatment for patients with PAD with significant functional, psychosocial and economic benefits. In current practice, there are no guidelines for exercise training and rehabilitation for patients who have progressed to CLI and have undergone revascularization. While it may be a challenge given the severity of disease and number of comorbidities in this patient population, it is great a disservice to deny these patients exercise rehabilitation given the possible advantages for their functional capacity, quality of life and even survival. Randomized controlled trials (RCT) are necessary to determine the precise role of exercise rehabilitation in patients with CLI. An RCT will provide guidance for regarding exercise tolerance, appropriate exercise modalities as well as the challenges and benefits of exercise rehabilitation in this critically ill population.

Objectives:

The aim of this pilot study is to develop a better understanding of the role for supervised exercise rehabilitation programs (SEP) in CLI patients after revascularization.

Our key objectives are as follows:

- 1) Our primary objective is to show that a 12-week SEP will improve functional capacity and quality of life in patients with CLI after revascularization. We will assess the feasibility for completion of a 12-week SEP in patients with CLI who have undergone revascularization.
- 2) Our secondary objective is to monitor major adverse limb events (MALE) and survival in patients who complete a 12-week SEP after revascularization.

Hypotheses:

- 1) We hypothesize that PAD-CLI patients who participate in an exercise rehabilitation after they have undergone revascularization will have a greater improvement in functional capacity and quality of life compared with patients treated with best medical therapy alone.
- 2) We hypothesize that PAD-CLI patients who participate in an exercise rehabilitation after they have undergone revascularization will have fewer MALE and improved survival compared with patients treated with best medical therapy alone.

OUTCOME MEASURES:

Primary outcome measures:

Our primary outcome measure for this project will be change in functional capacity as measured by a 6-minute walking test (6MWT) or maximal pain-free walking distance on a treadmill.

Secondary outcome measures:

- 1) Quality of life based on questionnaires validated for patients with PAD, the SF-36 and VQ6
- 2) Completion of a 12 week supervised exercise program

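### Patients who stop the exercise programme are assured only an interview at week 12; the plan does not say that they are still walk-tested or analysed as randomised

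*Combined protocol and SAP*

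**What the plan says.** All references are to the combined protocol and SAP.

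- **Patients who stop.** Under the heading "FOLLOW UP OF PATIENTS WITHDRAWN FROM STUDY" there is one rule: "Patients who withdraw or do not complete the program will be contacted and interviewed at the end of the 12 week study period". Its stated purpose is "to understand why they were unable to complete the training program". The rule covers both leaving the study and not finishing the programme, and mentions no walk test, questionnaire or ABI.
- **General test schedule.** Under Pre/Post Testing, Functional Capacity: "we will measure walking performances at the first exercise session and after 12 weeks". This is neither limited to completers nor expressly extended to those who stop. ABI and duplex are also set for 12 weeks, and the quality-of-life questionnaires for the first and last visits.
- **Other interviews.** Under Quality of Life, the investigators will "perform an interview and survey at the mid-term and at the completion of exercise program for the SEP group".
- **Primary outcome.** "change in functional capacity as measured by a 6-minute walking test (6MWT) or maximal pain-free walking distance on a treadmill". The first hypothesis is a between-arm one: exercise patients "will have a greater improvement in functional capacity and quality of life compared with patients treated with best medical therapy alone".
- **Analysis.** Under Statistical Analysis: "Results at baseline and 12 weeks will be compared using a paired t-test". No analysis population, intention-to-treat statement or missing-data rule appears anywhere.
- **Later follow-up.** The annual visits in Long-Term Follow-Up list no walk test.

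**The concern.** The one provision written for people who stop exercising treats them like people who have left the study, and secures only their reasons. A coordinator could reasonably follow it and arrange no week-12 test. The walking result would then be lost for good, because no later visit measures it.

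The non-completion part of the rule can apply only to SEP. BMT patients receive activity advice and a log, not a programme that they can fail to complete. If SEP stoppers go unmeasured while BMT patients who ignore the advice are tested as usual, the comparison sets SEP completers against something close to the whole BMT arm. That is no longer the randomised comparison. If people who stop tend to be those who tolerate or benefit from exercise least, the result leans towards SEP in both walking distance and quality of life.

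The patients at issue are alive, able to walk and already being contacted in the right week. This is separate from how death or amputation should be handled.

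**Working it through.** **Step 1. What the text secures at week 12.**

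| Patient | General test schedule | Withdrawal section |
|---|---|---|
| SEP, completes | applies | does not apply |
| SEP, stops but can walk | not excluded, not named | interview on reasons |
| BMT, ignores activity advice | not excluded, not named | does not apply |
| Either arm, withdraws | not excluded, not named | interview on reasons |

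Rows two and three have the same status under the general schedule. They differ because a more specific provision exists for row two, and it names only an interview.

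**Step 2. Effect on the analysis.** A comparison of baseline with week 12 in the same patient needs both values. Without a week-12 walk the patient contributes nothing, and no stated rule brings the patient back.

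**Step 3. The plan's own figure.** Sample Size gives 64 patients, 80% power, two-sided 0.05, and a 20% greater increase in 6MWT distance. Randomization splits this as 20 + 44 = 64. No SD is given, so 64 cannot be derived forwards. Backwards, assuming 32 per arm:

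- standardised difference = (1.960 + 0.842) × √(2/32) = 0.70
- if 20% means 20 points of baseline, SD = 20 / 0.70, about 28.5 points
- check: 2 × (28.5/20)² × 2.802² = 31.9, so 32 per arm and 64 in total

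The SD of 28.5 points is therefore implied, not documented.

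**Step 4. Size of the possible bias.** Let p be the fraction of SEP patients who stop and are not measured, C the completers' gain over BMT, and S the stoppers' gain over BMT. With BMT fully measured:

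- effect in all randomised patients = (1 − p) × C + p × S
- overstatement by completers alone = p × (C − S)

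Assume a 300 m baseline, so C = 20% × 300 = 60 m. The baseline, p and S are all assumptions.

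| p | S = 0 | S = 60 m (stopping unrelated to outcome) | S = 90 m (stoppers do better) |
|---|---|---|---|
| 10% | 0.10 × 60 = 6 m | 0 | 0.10 × (−30) = −3 m |
| 20% | 12 m | 0 | −6 m |
| 30% | 18 m | 0 | −9 m |

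With S = 0 the overstatement is 10–30% of the 60 m target. On the points scale it is 2, 4 and 6 of 20 points.

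**Step 5. False-positive rate if SEP has no true effect.** Assume SD 28.5 points, 32 BMT and 32 × (1 − p) SEP patients measured, and unmeasured stoppers 20 points worse than completers. The bias is p × 20 and the standard error is 28.5 × √(1/32 + 1/(32(1 − p))).

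- p = 10%: bias 2, standard error 7.32, rejection rate about 6%
- p = 20%: bias 4, standard error 7.56, about 8%
- p = 30%: bias 6, standard error 7.85, about 12%

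The nominal rate is 5%. With a gap of 10 points instead of 20, the rates are about 5%, 6% and 7%.

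**Step 6. If the loss is unrelated to outcome.** There is no bias, only lost precision. Power for 20 points falls from 80% to about 78%, 75% and 72% at p = 10%, 20% and 30%.

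**The case against.** The strongest reply is that the withdrawal section never says the walk test is withheld. The general schedule is not restricted to completers, and neither is annual follow-up. The SEP barriers interview is tied to the middle and end of the programme, and a patient who stops never reaches the end. The withdrawal section may simply fill that gap with an extra contact that replaces nothing. Moreover, anyone who relies on the general schedule to say that inactive BMT patients are tested must explain why it does not cover inactive SEP patients.

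This stands to the following extent. A reader might infer that the protocol bars stoppers from testing, or excludes them from the primary analysis. The documents state neither: the first is an inference from silence, the second a likely consequence of a paired comparison with no rule for missing values. But the reply does not resolve the ambiguity. The specific provision sits under a heading for withdrawn patients and names only an interview. A last visit is undefined for someone who stops early, and the secondary objective is worded for patients who finish the programme.

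Three further limits are accepted:

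- Withdrawal can occur in either arm of this unblinded trial, so it is too strong to say that only SEP loses outcomes. Losses in BMT could offset or reverse the bias.
- No attrition figure is given. Eligibility requires availability for all sessions and excludes exercise-limiting comorbidity, so frequent stopping cannot be presumed.
- Phase I is aimed at feasibility and safety, for which an interview on reasons is apt. Each SEP stopper is 10% of that arm (1 of 10), but the walking comparison is the Phase II objective.

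**Conclusion.** The concern holds as an unresolved ambiguity with a real route to bias. The two sections must be reconciled, and analysis as randomised must be stated. If the withdrawal section is followed alone, SEP stoppers' primary outcome is lost and cannot be recovered later. The loss falls mainly, not solely, on SEP.

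A reader might conclude that the SEP result is flattered. The documents do not support that as fact, because they give no drop-out rate, SD or outcome for stoppers. The 6–18 m illustration rests on an assumed 300 m baseline, 10–30% stopping, no gain over BMT in stoppers, and a fully measured BMT arm. It is zero if stopping is unrelated to outcome, and slightly reversed if stoppers do better.

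Larger figures can be constructed. A 100 m gap at 30% stopping gives 30 m, half the target. But with completers 60 m ahead of BMT, stoppers would then have to finish 40 m behind BMT, and nothing in the documents suggests that. This is best treated as a cheap improvement to make before enrolment.

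**What to change.** Rewrite the withdrawal section to separate stopping the programme from withdrawing consent. Suggested wording:

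*A patient who stops or does not finish the SEP remains in the study. The patient is invited to the same 12-week assessments as every other patient (6MWT, treadmill test, SF-36, VascuQol, ABI and duplex), in addition to the interview on reasons, and continues annual follow-up. Only withdrawal of consent ends data collection. All patients are analysed in the arm to which they were randomised.*

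Add a cross-reference under Pre/Post Testing so that the 12-week schedule plainly covers all randomised patients. Under Statistical Analysis, add a rule for week-12 values that are still missing, with a sensitivity analysis.

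**Cost.** Some protocol wording and one set of week-12 assessments for patients already contacted that week. Travel to the exercise facility is already reimbursed under Ethical Considerations. Treatment does not change.

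**Downside.** Some patients will decline, so some loss will remain. The estimated SEP effect may also be less favourable than in completers. On the assumptions used above (SD 28.5 points, completers gain 20 points, stoppers gain nothing), the all-randomised effect is 18, 16 or 14 points at 10%, 20% or 30% stopping. Power with all 64 measured is then about 71%, 61% or 50%. The attrition adjustment promised under Sample Size should take this dilution into account.
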